14.4 Analysis of Secondary Endpoints

As a secondary outcome, we will include an analysis that examines the change associated with the 7-day treatment with 0.9% saline. Our secondary analysis is to determine the characteristics of participants that respond to NAC. We will classify participants in four groups based on their post-bronchodilator FEV1 in response to NAC. FEV1 of 0-4% change will define non-responders and FEV1 of 5-9%, 10-14%, or > 15% will define the 3 categories of responders. We will examine NAC responders and non-responders to determine if baseline CT mucus scores, lung function measures, or sputum G' measures predict treatment response. We will construct ROC curves to determine the CT score that predicts NAC response thereby identifying a CT biomarker for future thiol saccharide trials. In addition, we will examine how the CT mucus score changes with NAC treatment using a subset of the participants following second period treatment. Finding a decrease in CT score in the 20% NAC group compared to the placebo group will provide support for

 our hypothesis that NAC improves lung function by decreasing intraluminal mucus. Other analyses will be to examine the effects of treatment on sputum elasticity (G').

Safety and tolerability data will be summarized by treatment group.

Adverse event rates will be coded by body system and MedDra classification term. Adverse events will be tabulated by treatment group and will include the number of patients for whom the event occurred, the rate of occurrence, and the severity and relationship to study drug.

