3.2 Secondary Objectives

The secondary objectives are to assess the clinical efficacy as measured in a subgroup of participants by the change in CT mucus score from baseline to end of treatment, and identify characteristics of those participants who benefit from mucolytic treatment.

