8.1.2 Medication Withholding

Bronchodilator reversibility will be used to establish eligibility at Visits 2, 5, and 8. Since some asthma medications can blunt the response to bronchodilators, we will ask that participants withhold these medications according to the guidance provided in Table 2.

Version #:1.5 Version Date: 8/5/2016 Page 20 of 41

Table 2. Medication Withholding Parameters

Medication	Withholding period
Leukotriene modifiers	24h
Ultra-long-acting bronchodilators (indacaterol, tiotropium)	24h
Long-acting beta-agonists	12h
Theophylline	12h
Short-acting anticholinergic	6h
Short-acting beta-agonists	4h

Participants will be evaluated at visit 1, without any medication holds, to establish the safety of withholding asthma medications. If a study clinician feels the participant is not clinically stable enough to withhold medications, they may shorten the guidance (with appropriate documentation on the Visit 1 CRF Physician Attestation section) or they may excuse the participant from some or all of the medication withholds.

Participants are reminded of these medication holds by phone 24 hours prior to their medication withholding visits and instructed to resume all medications should symptoms develop in the period prior to the visit.

Associated risks of medication withholding include a worsening of asthma control or asthma exacerbation. To mitigate these risks, participants are given clear instruction to resume asthma medications if symptoms arise.

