14.3 Analysis of Primary Endpoint

The primary outcome is the % change in FEV1 from the start to the end of the treatment period (either placebo or 20% NAC). The first analysis will be to test the assumption of negligible carryover effects from study period 1 to period 2. We will compare the sum of the outcome values measured in the two periods for each participant across the 2 sequence groups (placebo-20% vs. 20%-placebo) using an unpaired t-test. After no or negligible carryover effect has been confirmed, we will test for the difference in treatment effects between placebo and 20% NAC using a paired t-test.

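### The NAC responder label and the CT-score ROC make no stated use of the saline period, so the ROC alone cannot show that CT score predicts benefit from NAC

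*Combined protocol and SAP*

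**What the plan says.** Section 3.2 sets a secondary objective to "identify characteristics of those participants who benefit from mucolytic treatment". Section 14.6 gives the choice of a CT score as a response biomarker as part of the reason for 30 participants.

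Section 14.4 carries this out in two steps:
- The label: "We will classify participants in four groups based on their post-bronchodilator FEV1 in response to NAC". The classes are: "FEV1 of 0-4% change will define non-responders and FEV1 of 5-9%, 10-14%, or > 15% will define the 3 categories of responders".
- The ROC: "We will construct ROC curves to determine the CT score that predicts NAC response thereby identifying a CT biomarker for future thiol saccharide trials".

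The same section says that "we will include an analysis that examines the change associated with the 7-day treatment with 0.9% saline", but as a separate secondary outcome. Its NAC-versus-placebo comparison of CT concerns change in CT score, not the responder label. The paired NAC-versus-placebo contrast in FEV1 belongs to the primary analysis (Section 14.3).

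Section 14.4 names no visits for the label. They can be inferred: Section 14.3 defines percent change from start to end of a treatment period, and Sections 9.4, 9.5, 9.7 and 9.8 schedule post-bronchodilator spirometry at visits 4, 5, 7 and 8.

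**The concern.** Benefit from NAC is a contrast with what the same person would have done on saline. The two-period crossover (Section 4.1) observes both changes in each completer, yet the label is described from one of them. If CT score were related to seven-day FEV1 change whatever was nebulized, the NAC-period ROC would show a useful-looking curve, and nothing in the planned analysis would reveal that saline gives the same curve.

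The cut-off is meant to guide later thiol-saccharide trials, so a score that is only prognostic could be carried forward as a predictor of drug response.

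A smaller matter is that the printed classes do not cover a fall in FEV1 or a change of exactly 15%.

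**Working it through.** **The plan's own figure.** Section 14.6 gives SD 19, difference 10, two-sided alpha 0.05, 80% power and n = 30. As a paired or single mean change, n = (19 × (1.960 + 0.842) / 10)² = 28.3, so 29. At n = 30 power is 82.2% (normal) or 79.6% (noncentral t). The figure reproduces, but it concerns the mean effect. The documents give no figure for the label or the ROC. They also do not say that the SD of 19 is post-bronchodilator or per period, so an assumed SD of 8 is shown beside it.

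**1. Chance responders.** Model the NAC-period change as Normal(μ, SD), with response meaning 5% or more.

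| SD | μ | fall (<0) | 0 to <5 | ≥5 |
|---|---|---|---|---|
| 8 | 0 | 0.500 | 0.234 | 0.266 |
| 19 | 0 | 0.500 | 0.104 | 0.396 |
| 8 | 10 | 0.106 | 0.160 | 0.734 |
| 19 | 10 | 0.299 | 0.097 | 0.604 |

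At μ = 0 with no NAC effect, 30 × 0.266 = 8 and 30 × 0.396 = 12 participants are labelled responders. A change that rounds to exactly 15% has probability 0.009 to 0.041 over these four cases.

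**2. A mean shift common to both periods (assumed −5 to +5 points), no NAC effect.** The share labelled responders runs from 0.106 to 0.500 (SD 8) or 0.299 to 0.500 (SD 19). The mean NAC-minus-saline difference stays at 0. A shift that is the same for everyone and unrelated to CT score moves the count but leaves the expected AUC at 0.50.

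**3. When the AUC would mislead.** Assume no NAC effect and a correlation r between CT score and FEV1 change that is equal in both periods (SD 19, mean 0, 400,000 draws, falls as non-response).

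| r | NAC period | saline period | NAC minus saline |
|---|---|---|---|
| 0.2 | 0.591 | 0.592 | 0.500 |
| 0.3 | 0.638 | 0.636 | 0.502 |
| 0.4 | 0.684 | 0.685 | 0.500 |
| 0.5 | 0.731 | 0.734 | 0.498 |

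The NAC ROC alone cannot reveal the problem. The saline ROC or the difference can.

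**4. Do the documents supply such an r?** No. Section 1.1 links plugs to FEV1 level, not to seven-day change, and the entry limits on CT score and FEV1 in Section 6.2 narrow both ranges. One mechanism can be modelled: the same litre change is a larger percentage of a lower baseline. The inputs are all assumed: baseline 2.3 L, SD 0.6, kept if above 1.0 L; CT–baseline correlation −0.3 to −0.7; litre change independent of CT score, with SD 8% or 19% of 2.3 L and mean −0.10, 0 or +0.10 L. The AUC is then 0.508 to 0.555, and a Mann-Whitney test gives p < 0.05 in 4.3 to 7.1% of samples of 30. That is not a material source.

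**5. What a net analysis costs.** The SD of the difference is SD × √(2(1 − ρ)), where ρ is the within-person correlation of the two changes. Label the difference at 5% with no NAC effect:

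| ρ | SD of difference (per-period SD 19) | labelled, SD 19 | labelled, SD 8 |
|---|---|---|---|
| 0 | 26.9 | 0.426 | 0.329 |
| 0.25 | 23.3 | 0.415 | 0.305 |
| 0.5 | 19.0 | 0.396 | 0.266 |
| 0.75 | 13.4 | 0.355 | 0.188 |

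A net label cuts chance labelling only when ρ exceeds 0.5.

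**6. Precision at n = 30.** For a regression with one added covariate, the partial correlation detectable with 80% power is tanh((1.96 + 0.84)/√(30 − 3 − 1)) = tanh(2.80/√26) = 0.50. By Hanley-McNeil, an observed AUC of 0.70 has a 95% CI of 0.50 to 0.90 with 12 responders and 18 non-responders, and 0.47 to 0.93 with 8 and 22.

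**The case against.** The best defence is that no harm to the ROC is demonstrated. The misleading AUCs in step 3 follow from a correlation that was assumed, and the one mechanism modelled gives almost nothing. That stands: the point is about what the analysis can distinguish, not about a known bias.

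A net definition is also not free. Suppose CT score correlates 0.4 with NAC change and 0 with saline change, with equal SDs and ρ = 0 (all assumed). Its correlation with the difference is then 0.4/√2 = 0.28, and Fisher-z power at n = 30 falls from about 60% to 33%. This stands as well, and is why the net analysis should be added and the planned label kept.

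The wording may simply be short. Response to NAC may be meant net of saline, falls are naturally read as non-response, and the visits can be inferred. The five-day saline run-in (Section 4.1) also means that participants given NAC first start from a baseline already on nebulized saline, which partly removes a saline effect in that sequence, though not in period 2. Finally, Section 14 promises a detailed SAP. All of this is fair, but none of it puts the saline change into the label or the ROC, and the SAP is where the fix belongs.

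**Conclusion.** The concern holds as a limited point about a secondary analysis. As written, the ROC cannot tell whether CT score predicts benefit from NAC or FEV1 change on either treatment. With no NAC effect, 27% to 40% would be labelled responders, given normal changes, zero mean, falls as non-response, and an SD between an assumed 8 and the plan's 19.

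A reader might infer more, but the documents do not support it:
- **That the ROC will produce a false biomarker.** The documents give no correlation between CT score and FEV1 change, so the size of any false signal is unknown.
- **That medication holds distort the changes.** Section 8.1.2 says "Bronchodilator reversibility will be used to establish eligibility at Visits 2, 5, and 8" and "we will ask that participants withhold these medications according to the guidance provided in Table 2". Visits 5 and 8 end the two periods, and the start visits 4 and 7 are not named. A start-to-end asymmetry is only an inference: Section 8.1.10 schedules reversibility at visits 2 to 8, clinicians may excuse holds, the Appendix B table is not available to check, and no effect on post-bronchodilator FEV1 is given. A shift equal for all would in any case leave the AUC unchanged.
- **That up to half of participants would have no class.** This needs the literal reading of the classes. Four groups with one non-responder group points to pooling falls, so the gap is mostly wording.
- **That the responder label must be replaced by a net one.** Step 5 shows a trade-off.

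**What to change.** In the SAP, before unblinding:
1. Keep the planned classes and ROC. State that every change below 5%, including falls, is non-response, and that the top class is 15% or more.
2. Add, as the analysis that supports any biomarker conclusion, a linear regression of each participant's NAC-period minus saline-period percent change in post-bronchodilator FEV1 (visits 4 to 5 and 7 to 8) on continuous baseline CT mucus score. Include a sequence term, which absorbs a period effect. Report the slope and its 95% CI.
3. Report the same ROC for the saline-period change beside the NAC ROC.
4. Label the ROC cut-off exploratory and give its confidence interval.

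The cost is SAP text, one regression and one extra ROC, with no new data or visits. Section 14 allows the SAP to modify the plan, and Section 7.2 keeps the blind until database lock, so this can be fixed in advance.

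The downsides should be stated too. Participants with only one period drop out of the regression. The difference is noisier than a single change if the within-person correlation is below 0.5. It relies on negligible carryover, as the primary test does ("After no or negligible carryover effect has been confirmed"). And 30 participants give 80% power only for a partial correlation of about 0.50, so a null slope would not rule out a useful score.

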7 STUDY TREATMENTS

7.1 Method of Assigning Participants to Treatment Groups

Up to 30 eligible patients will be randomly assigned to receive either the experimental treatment (20% NAC) or the placebo treatment (0.9% saline) during period 1 in a 1:1 ratio using a SAS-based computer-generated randomization scheme developed by the study data manager. The investigational pharmacy, who will supply the prepared study medication packets, will complete a randomization worksheet at the end of run-in and log group assignment. This log will be shared with investigators upon study completion or in the event of a serious safety concern.

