12.4 Replacement of Participants

Participants who withdraw from the study treatment will be replaced.

Participants who withdraw from the study will be replaced.

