14.6 Sample Size and Randomization

We propose a sample size of 30, which will provide us with the power to examine the effect of NAC in a subgroup of individuals with asthma who have CT evidence of intraluminal mucus and to identify the CT mucus score that performs best as a biomarker of treatment response to NAC. Participants will be enrolled if their CT mucus scores are >3.0. To calculate sample size for the one-week treatment period study, we used FEV1 measures from 219 adults with asthma published in Corren et al. NEJM, 2011¹. The authors found that the standard deviation for the change in FEV1 in liters from day 1 to day 7 was 19%. Using a standard deviation of 19 and a two-sided alpha of 0.05, we calculate a sample size of 30 to have 80% power to detect a change in FEV1 of 10% (a reasonable effect size because early studies of Pulmozyme in CF reported a 10% increase in FEV1 at day 3 of treatment).

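### Cutting one noisy 7-day FEV1 change into a responder label weakens the CT-score biomarker analysis; a regression on the continuous change should lead.

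*Combined protocol and SAP*

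**What the plan says.** Section 3.2 makes it a secondary objective to identify who benefits from mucolytic treatment. Section 14.4 sets the method. Participants are grouped by their post-bronchodilator FEV1 response to NAC: "FEV1 of 0-4% change will define non-responders and FEV1 of 5-9%, 10-14%, or > 15% will define the 3 categories of responders". Baseline CT mucus score, lung function and sputum G' are then examined as predictors of response, and the plan continues: "We will construct ROC curves to determine the CT score that predicts NAC response". The resulting CT score is intended as a biomarker for later trials. No subtraction of the saline-period change is stated, and a fall in FEV1 is given no category.

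Section 14.6 claims that 30 participants give power to find the best-performing CT score. Its sample-size calculation reports that "The authors found that the standard deviation for the change in FEV1 in liters from day 1 to day 7 was 19" percent, and proceeds "Using a standard deviation of 19 and a two-sided alpha of 0.05". The design in section 4.1 is a two-period crossover, so each person contributes one NAC period. Section 14 mentions neither misclassification by the label nor an expected AUC, and it plans no analysis of the continuous response against CT score.

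**The concern.** The lowest responder cut is 5 points and the bands are 5 points wide, while the plan expects a single 7-day change to vary with an SD of 19. If much of that SD is variation unrelated to NAC, the label sorts participants largely by noise. Enrolling more people would make the estimated AUC more precise but would not correct the labels.

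The CT cut-off is meant to guide selection in later trials. A cut-off read from an ROC curve with a badly mislabelled outcome could be wrong, and a useful marker could be missed. The continuous FEV1 change, which the trial collects anyway, keeps the information that the label discards.

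**Working it through.** **Inputs.** SD 19, two-sided alpha 0.05, difference 10, power 80%, N = 30 (section 14.6); paired t-test (section 14.3); responder cut of 5 (section 14.4). The documents give no distribution of individual NAC effects, so every effect pattern below is an assumption.

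**The plan's own figure.** n = (SD × (z0.975 + z0.80) / difference)² = (19 × (1.960 + 0.842) / 10)² = 28.3, so 29. Exact paired-t power at n = 30 is 79.6%. N = 30 is therefore reproduced, with 19 acting as the SD of the paired difference.

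**False responders.** The cut is 5/19 = 0.26 SD. For a participant with no NAC effect, a normal change with mean 0, and falls counted as non-response:
- SD 19: 1 − Φ(5/19) = 39.6%
- SD 13.4: 1 − Φ(5/13.4) = 35%. This is 19/√2, the single-period SD if 19 is the SD of a difference between two uncorrelated periods.
- SD 10: 1 − Φ(5/10) = 31%

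With a true 10-point gain at SD 19, the chance of being labelled a responder is 1 − Φ(−5/19) = 60.4%. With no effect, 1 − Φ(15/19) = 21% still reach 15 or more, so the bands do not separate degrees of response well.

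**AUC of a perfect yes/no marker.** Let half the participants gain a fixed amount and half gain nothing, with noise SD 19. AUC = (1 + TPR − FPR)/2, where TPR and FPR are the proportions of true gainers among labelled responders and labelled non-responders.
- Gain 10: TPR = 0.604/(0.604 + 0.396) = 0.604 and FPR = 0.396, so AUC = 0.604.
- Gain 20: TPR = 0.785/(0.785 + 0.396) = 0.665 and FPR = 0.215/(0.215 + 0.604) = 0.262, so AUC = 0.70.
- Gain 5 gives 0.55 and gain 15 gives 0.65.
- Gain 10 with noise SD 10 gives 0.69.

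**Effect of moving the cut.** With half gaining 10 at SD 19, the AUC is 0.604, 0.605 and 0.607 at cuts of 5, 10 and 15. The false-responder rate falls (39.6%, 29.9%, 21.5%), but the AUC barely changes.

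**Power at n = 30.** These come from 4,000 simulated trials per scenario: linear regression on the continuous change, against a chi-square or Mann-Whitney test on the 5%-or-more label. CT score is uniform over 3.5 to 19 where the gain is graded.

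| Assumed pattern | SD | Continuous | Label |
|---|---|---|---|
| Half gain 20, half 0 | 19 | about 80% | about 60% |
| Gain rises 0 to 30 across CT 3.5 to 19 | 19 | about 65% | about 40% |
| Gain rises 0 to 20 across CT 3.5 to 19 | 10 | about 83% | about 58% |
| Half gain 10, half 0 | 19 | about 28% | about 20% |

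**The case against.** **An AUC ceiling near 0.6.** A reader might infer that even a perfect CT marker could never do better than about 0.6. The documents do not support this, because they give no distribution of individual effects. The figure needs half the participants to gain 10, half to gain nothing, and all of the 19 to be noise. If the plan's mean effect of 10 comes from half gaining 20, the AUC is 0.70. With noise SD held at 19, the patterns tried run from about 0.55 to 0.79, the top value being for a continuous marker of normally distributed effects with SD 15.

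**The 5% cut as the cause.** A reader might also blame the cut and expect a higher one to help. Only the false-responder rate depends on the cut; the low AUC comes from noise in a single change. The continuous outcome carries that noise too. With half gaining 10, a perfect marker explains only 25/(25 + 361) = 6.5% of the outcome variance, which is why the regression has only about 28% power. This objection stands and limits what the fix can promise.

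**A good marker would look useless.** This goes too far. If half gain 20, the labelled analysis still has about 60% power.

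**Applying SD 19 to this label.** Section 14.6 describes the SD both in liters and as a percentage and does not say it is post-bronchodilator. This stands, so the 40% is conditional. The rate is still 31% at SD 10 and 27% at SD 8.

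**Negative changes.** Counting them as non-response is an assumption. Read literally, section 14.4 leaves half of no-effect participants unclassified, and 0.396/0.5 = 79% of those classified would be responders. The 40% is the reading kinder to the plan.

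**Context.** This is a secondary analysis with no decision rule, and section 14 promises a detailed SAP. That lowers the severity, but section 14.6 does claim power for this aim.

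**Conclusion.** The point holds in a conditional form. On the plan's own SD, and with falls counted as non-response, about 40% of participants with no NAC effect would be labelled responders; the rate is 31% to 35% at SDs of 10 to 13.4. Under a half-and-half pattern at SD 19, a perfect marker would reach an AUC of about 0.60 for a 10-point gain and 0.70 for a 20-point gain. These values depend on assumed effects and are not general limits.

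The firmest result is the comparison of methods. The continuous analysis had more power in every scenario checked, by about 20 to 25 percentage points in three of the four and about 8 in the fourth. That ordering held at SD 10 as well as SD 19, so the recommendation does not rest on 19 being right. If half gain 10 at SD 19, the continuous analysis is better but still weak. The change should be made, but the primary analysis is unaffected.

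**What to change.** In the SAP, make the main predictor analysis a linear regression of the continuous within-participant post-bronchodilator FEV1 response on continuous baseline CT score, and report the slope with its 95% CI. Keep the responder bands, the ROC curves and any CT cut-off as descriptive, and say how a fall in FEV1 is classified.

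State whether the response is the NAC-period change alone or that change minus the saline-period change. Subtraction does not automatically reduce the noise. If each period's SD is 19, the SD of the difference is 19 × √2 = 26.9 with uncorrelated periods (false-responder rate 42.6%), and it stays at 19 with a correlation of 0.5.

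The cost is SAP wording and a regression on data already collected, with no new visits or participants. There are three downsides: a linear form is assumed, no responder percentage leads the report, and a confidence interval for a CT threshold may be unbounded when the slope is not significant. With power of about 65% in the 0-to-30 scenario, that would happen in roughly 35% of trials, so any threshold should be labelled exploratory. The SAP should also acknowledge that power is low if effects are modest, rather than repeat the claim in section 14.6.

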1.1 Overview of Clinical Studies

Against this background, the preliminary data we show in Figs 1 and 2 are very important, because we show how CT lung images can reveal mucus plugs in chronic severe asthma and how these plugs are associated with lower lung function. Specifically, we use CT imaging to uncover that a majority (58%) of asthmatics in the NHLBI Severe Asthma Research Program (SARP) have at least one lung segment with a mucus plug and 27% have more than four lung segments with mucus plugs. Notably, asthmatics with a high mucus scores achieve a post albuterol FEV1 > 80% much less frequently than asthmatics who have a zero mucus score (Fig 3).

Examined another way, we find that all asthmatics with an FEV1 \leq 60% after

[figure not shown]

Figure 2. A. The CT mucus segment score is usually 0 in health but many asthmatics enrolled in the NHLBI Severe Asthma Research Program have scores above 0 with some as high as 15-19. B. The frequency distribution of mucus score in asthma shows that 42% of patients have a score of 0 (zero mucus score); among the remaining 58% of asthmatics, the median mucus score was 3.5, and we classified score between 0.5 and 3.5 as "low" and above 4.0 as "high".

albuterol treatment have abnormal mucus scores, whereas the majority of asthmatics with an FEV1 >80% with albuterol treatment have zero or low mucus scores (Fig 3). These data clearly implicate mucus plugs in the pathogenesis of airflow obstruction in asthma. One reason why this role for mucus plugging has been underappreciated in chronic severe asthma is that mucus-related symptoms are both insensitive and non-specific indicators of mucus. This is well illustrated in the table, which presents data for the prevalence of mucus-related symptoms in asthmatics with different mucus score categories. None of the mucus-related symptoms were significantly different in the zero, low or high mucus subgroups, and it is clear that these symptoms have very limited utility to investigate the

role of mucus in asthma or to identify asthmatics who might benefit from mucus-directed treatments.

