1.2 Overview of Non-Clinical Studies

To test the hypothesis that airway mucus in asthma has abnormal elasticity, we performed rheology on induced sputum from 40 asthmatic participants recruited to UCSF as part of the SARP. The majority of these asthmatic participants (65%) had severe asthma. We compared the elastic modulus (G') of these participants to induced sputum G' in 11 healthy controls. We found that the G' in the asthmatic group was significantly higher than normal (Fig 4A). Notably, we found a strong inverse correlation between G' and FEV1 % (Fig 4B). This finding suggests that stiff mucus in the airway of asthmatics could be a mechanism of mucus

[figure not shown]

Figure 3. Mucus scores in asthmatics with different FEV1 values (post 6-8 puffs of albuterol). Note that all asthmatics with an FEV1 <60% have abnormal mucus scores.

impaction of airways and airflow obstruction. It further suggests that decreasing mucus G' could be a treatment strategy to improve airflow. To determine if the G' of asthmatic sputum is a result of excessive mucin disulfide bridges (as it is in CF), we measured the G' in a subgroup of 6 asthmatics before and after the addition of n-Acetylcystine (NAC) (61mM). We found that NAC markedly decreased the G' at both 2 minutes and 12 minute

[figure not shown]

Figure 4. A. Sputum in asthma has an increased elastic modulus (G'). B. The G' of asthma sputum is significantly and inversely related to FEV1 (*ex vivo* data from 40 asthmatics and 11 healthy participants [red dots])

time-points after the addition of NAC (Fig 4A & B). This indicates that disulfide bonds are a mechanism of high sputum elasticity and a target for mucolysis in asthma, and it suggests thiol-based compounds as a rational mucolytic strategy.

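### A ROC on CT score alone cannot separate CT from starting FEV1 when response is a percent change in FEV1; the false CT signal is small, but the biomarker claim needs a test of what CT adds to FEV1

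*Combined protocol and SAP*

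**What the plan says.** Section 14.4 (Analysis of Secondary Endpoints) sets out the responder analysis: "We will classify participants in four groups based on their post-bronchodilator FEV1 in response to NAC". The classes are percentages: "FEV1 of 0-4% change will define non-responders and FEV1 of 5-9%, 10-14%, or > 15% will define the 3 categories of responders". Section 14.4 does not name the denominator. The natural reading comes from Section 14.3, "The primary outcome is the % change in FEV1 from the start to the end of the treatment period", which makes it the FEV1 at the start of the period.

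Responders and non-responders are then compared "to determine if baseline CT mucus scores, lung function measures, or sputum G' measures predict treatment response". For CT the plan goes further: "We will construct ROC curves to determine the CT score that predicts NAC response". The stated purpose is a CT biomarker for later thiol-saccharide trials, and Section 14.6 gives finding the best CT score as part of the reason for 30 participants.

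The protocol's own preliminary data link these predictors to FEV1. Section 1.1 describes "how these plugs are associated with lower lung function" and reports that "asthmatics with a high mucus scores achieve a post albuterol FEV1 > 80% much less frequently than asthmatics who have a zero mucus score". Section 1.2 states that "we found a strong inverse correlation between G' and FEV1" (as a percentage). No coefficient is given for either link.

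Section 14.4 contains no adjustment for baseline FEV1, no analysis of absolute change, and no comparison of CT with spirometry.

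**The concern.** When the outcome is a gain divided by starting FEV1, equal gains in litres give unequal labels. A participant with low FEV1 crosses a percentage threshold more easily than one with high FEV1. Baseline FEV1 can therefore look like a predictor of response when nobody benefits more than anybody else. Any variable correlated with FEV1 inherits part of that appearance, and the protocol says CT score and G' are such variables.

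A ROC on CT score alone cannot tell three situations apart: CT marks people who truly benefit more; CT stands in for low FEV1, which truly predicts benefit; or CT stands in for a small denominator. Only the first supports selecting patients by CT in a later trial. In the other two, spirometry would do as well or nothing has been found. Subtracting the saline-period response would not settle this, because the starting FEV1 stays in the denominator.

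**Working it through.** **The plan's own figure.** The documents give no calculation for the predictor analysis. The only related figure is the primary sample size in Section 14.6 (SD 19, difference 10, two-sided alpha 0.05, 80% power). The paired formula gives n = (19 × (1.960 + 0.842) / 10)² = 28.3, so 29. Noncentral-t power at n = 30 is 79.6%. The figure of 30 is reproduced as a paired calculation and is not affected by this point.

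**Equal gain, different label.** Percent change = gain / starting FEV1.
- Gain of 0.20 L: 0.20/1.5 = 13.3%; 0.20/2.0 = 10.0%; 0.20/3.5 = 5.7%. These fall in two different responder classes.
- Gain of 4 points of predicted, within the entry limit of FEV1 below 90% predicted: 4/50 = 8.0% (responder); 4/80 = 5.0%; 4/89 = 4.5% (below the 5% boundary).

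**How much passes to a correlated predictor.** A simulation gave every participant the same true gain, so the correct AUC is 0.50. None of these inputs is in the documents: starting FEV1 lognormal, mean 2.1 L, SD 0.65 L; gain 0.2 L; correlation of the predictor with log starting FEV1 of -0.3, -0.5 or -0.7; SD of the random part of the change set at 5, 10 or 19% of mean FEV1 (0.05 × 2.1 = 0.105 L, 0.10 × 2.1 = 0.21 L, 0.19 × 2.1 = 0.40 L). Response is a change above 10%.

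| Noise SD | AUC, corr. -0.3 | AUC, corr. -0.5 | AUC, corr. -0.7 | AUC, starting FEV1 itself |
|---|---|---|---|---|
| 5% | 0.57 | 0.61 | 0.66 | 0.73 |
| 10% | 0.54 | 0.56 | 0.59 | 0.63 |
| 19% | 0.52 | 0.54 | 0.55 | 0.57 |

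The rate of a falsely significant rank correlation at n = 30 (nominal 5%), for correlations -0.3 / -0.5 / -0.7, is 12 / 26 / 45% at 5% noise, 7 / 10 / 18% at 10% and 7 / 7 / 9% at 19%.

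**Other settings.**
- Mean FEV1 2.0 L, SD 0.6 L, common gain 0-0.2 L, change SD 0.15-0.25 L: CT AUC 0.53-0.60 for correlations -0.3 to -0.5. FEV1 read at a separate earlier visit gives 0.60-0.68.
- The same set-up at change SD 0.38 L (19% of 2.0 L): CT AUC 0.52 and 0.54.
- Restricted to the trial's entry limits, change SD 0.10-0.38 L: CT AUC 0.51-0.58, and 0.51-0.52 near 19%.
- A 5% cut instead of 10%: CT AUC 0.52-0.55 at change SD 0.15-0.25 L.

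**If the gain is proportional instead.** With the same percentage gain for everyone, CT AUC on percent change is 0.50. On points of predicted it is 0.42-0.49, a bias in the opposite direction.

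**Absolute change.** With a common litre gain and noise constant in litres, the AUC on change in litres is 0.50 and the false-positive rate about 5%. If noise grows with FEV1, a litre cut-off gives 0.49-0.60, while the correlation with continuous change stays at 0.00. A model of continuous change is therefore safer than any new cut-off.

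**Against sampling error.** With 15 responders and 15 non-responders, the standard error of a null AUC is √((15 + 15 + 1) / (12 × 15 × 15)) = √(31/2700) = 0.11. A bias of 0.01-0.04 is well inside that.

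**The case against.** The strongest case against is about size and remedy, and most of it stands.

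- *All three predictors are tied to the label by arithmetic.* A reader might infer this, but only FEV1 is. CT and G' are linked through correlations without published coefficients, from a broader cohort. The Section 1.1 contrast is with zero mucus scores, which this trial excludes (entry needs a score above 3). Entry also caps FEV1 below 90% predicted, and G' exists only above 50% (Section 8.1.12). These limits probably weaken both links.
- *Lung function would falsely predict response with an AUC of 0.69-0.75.* That needs the predictor to be the same Visit 4 or Visit 7 reading that starts the change, so that its error enters both sides. Section 4.1 lists baseline apart from end of run-in and the start of period 2, Section 8.1.14 puts baseline CT at Visit 2, and Section 14.2 takes baseline FEV1 at screening. The documents favour an earlier visit, though Section 14.4 does not say so.
- *Percent change is the wrong scale and should be replaced.* The documents do not establish whether benefit is additive or proportional. If proportional, percent change is neutral for CT and the replacement creates the reverse bias. Percent change also matches the primary endpoint.
- *The analysis is exploratory and a detailed SAP is still to come* (opening of Section 14). True, which makes this easy to settle now. It does not make a CT-only ROC able to support the intended conclusion.

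**Conclusion.** The point holds in a limited form. With similar gains in litres, the percent-change label favours participants with low FEV1, so baseline FEV1 can appear predictive with no differential benefit. CT score and G' share this to a small degree. For correlations of -0.3 to -0.5, the spurious CT AUC is about 0.51-0.60 (0.61 at the edge, with noise of only 5%), and about 0.51-0.54 if noise is near the 19% SD in Section 14.6. A stronger correlation, such as -0.7 for G', would give 0.55-0.66 across 19% to 5% noise.

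These sizes rest on assumed correlations, FEV1 spread and noise, and on an additive gain. The 19% is a published figure for change in FEV1, not necessarily for post-bronchodilator FEV1 in this population.

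The firmer conclusion needs none of those assumptions: a ROC on CT alone does not show that CT tells us more than spirometry. The primary analysis and its sample size are untouched.

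**What to change.** Keep the percent-change classes and add the following to Section 14.4 or the SAP:

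1. Report the AUC of baseline post-bronchodilator FEV1 % predicted beside the CT and G' AUCs.
2. Base any CT-biomarker claim on whether CT adds to baseline FEV1, for example in a model of continuous change with baseline FEV1 as a covariate, with a confidence interval.
3. Repeat the ROC with absolute change (litres or points of predicted) as a prespecified sensitivity analysis, and interpret the two scales together.
4. State that baseline lung-function predictors come from Visit 2 or 3, not from the Visit 4 or 7 reading that starts a treatment period, and name the denominator of the percent change.

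The cost is SAP wording and a little more analysis. Post-bronchodilator spirometry is already scheduled at Visits 2 and 3, so no new visit, scan or participant is needed. The limitation is precision: with 30 participants, added value will be estimated loosely, and the report should say so.
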